This phase III trial is planned to provide 90% power to detect a 25% increase in the rate of sustained recovery for an investigational agent compared to placebo at the 0.025, 1-sided level of significance. This requires 843 primary events (i.e., participants who achieve sustained recovery). Randomization of 1,000 participants, equally allocated to each investigational agent and placebo, followed for 90 days is estimated to result in the required number of primary events. The event target may be achieved earlier if more than 1,000 participants are enrolled. Sample size will be evaluated periodically by study team members who are blinded to interim results on treatment difference and may be increased to maintain power for the hypothesized difference in sustained recovery between the investigational agent and placebo.

Population

The study population consists of inpatient adults (\geq 18 years) who have had COVID-19 symptoms \leq 12 days. Initially, enrollment is restricted to disease severity stratum 1. After a pre-specified review by the DSMB for safety and futility, when approximately 150 participants

are enrolled per study arm, eligibility for randomization will be expanded to also include patients in disease severity stratum 2, subject to recommendations by the FDA and DSMB.

Stratification

Randomization is stratified by study site pharmacy; once enrolment is expanded to also include disease severity stratum 2, randomization will also be stratified by disease severity stratum.

Monitoring

An independent DSMB will review interim data on a regular basis for safety and efficacy. An initial futility assessment will be performed after the first 300 participants (150 in the active and 150 in the placebo arms) are enrolled and have Day 5 data; this initial assessment is based on two ordinal outcomes (pulmonary and pulmonary+ outcomes at Day 5). Afterwards, the DSMB will use pre-specified guidelines to identify agents with clear evidence of efficacy for the primary outcome and, if so, recommend unblinding of the trial results for that agent. Conversely, the DSMB may recommend discontinuation of an investigational agent if the risks are judged to outweigh the benefits or if futility assessments indicate that there is low probability that an investigational agent will achieve statistical significance for the primary endpoint of sustained recovery.

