stratified by disease severity at entry and by site pharmacy (as described in section 3 under "stratification"). Gray's test compares the cumulative incidence functions for *sustained recovery* between the treatment groups, taking into account the "competing risk" of death in analyzing *sustained recovery*. Gray's test with ρ =0 is the competing-risks analogue of the log-rank test.

Comments:

- 1. Comparisons will be presented such that recovery rate ratios (RRR) >1 denote superiority of the investigational agent.
- 2. For AZD7442, the primary analysis is hierarchical: the overall comparison between treatment groups is followed by a comparison within the subgroup of participants who are nAb seronegative at study entry (described in Appendix E).

Analyses for the *sustained recovery* endpoint require methods that take into account the competing risk of death, as participants may die before ever achieving *sustained recovery*. The *sustained recovery* outcome requires knowledge of a participant's residence status for at least 14 days after arriving "home" (as defined above).

- The cumulative incidence functions for sustained recovery will be estimated by treatment group, using Aalen-Johansen estimators.³ The estimates will be plotted over time, and tabulated at selected time points (days 15, 21, 28, 42, 60, 75, 90). The Aalen-Johansen estimator for a cumulative incidence function is the analogue of the Kaplan-Meier estimator in the presence of competing risks.
- The recovery rate ratio (RRR) for time to sustained recovery of the investigational agent versus control will be estimated, as a point estimate with a 95% CI, using the Fine-Gray model, stratified by disease severity at study entry and study site pharmacy.^{5,6} The corresponding p-value for RRR=1 versus the two-sided alternative will be calculated. The Fine-Gray method is the competing risks equivalent of Cox proportional hazards models; the RRR compares the cumulative incidence rates of *sustained recovery* between the study arms and is a sub-distribution hazards ratio (sHR).
- To aid in the interpretation of the estimated treatment difference, the median days to sustained recovery (through Day 90) will be estimated for the investigational agent and the control group. Medians will be compared using the Wilcoxon rank sum test or quantile (median) regression. Participants who die at any time up to Day 90 will be assigned 91 days.

Censoring:

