For the AZD7442 investigational agent, additional subgroup analyses will be carried out for the following subgroups defined at baseline; subgroups, hypotheses and analyses are described in Appendix E:

- SARS-CoV-2 vaccination status. Subgroups will be formed by vaccination status and by type of vaccine.
- Immunosuppressive state
- SARS-CoV-2 viral genome sequence and variant lineage.

As a **general rule**, subgroup analyses will be carried out using statistical models that are stratified by disease severity; for time-to-event analyses, stratified Fine-Gray or Cox proportional hazards models will be used, while for other outcomes, models will include the disease severity indicator as covariate. Global tests for heterogeneity of the treatment effect across subgroups will be carried out, by adding the interaction between the subgroup indicator and the treatment group indicator to a model that contains the treatment group indicator and subgroup variable as "main effects". In case the subgroup was formed by categorizing a continuous variable, the models used for the subgroup analyses will contain the (continuous) subgroup variable as covariate, and the interaction term in the expanded model will be formed between the subgroup indicator and the continuous variable.

Subgroup analyses for the primary endpoint of **time to sustained recovery** will use the Fine-Gray model (with death as competing risk), stratified by disease severity at study entry. Within each subgroup, the number and percent of recovered participants and median time to recovery will be calculated by treatment group, and sHRs with 95% CIs comparing the investigational agent versus control will be estimated. Global tests for heterogeneity of the treatment effect across subgroups will be carried out, by adding the interaction between the subgroup indicator and the treatment group indicator to the model that contains data across all subgroups. Median time to recovery will be estimated using Aalen-Johansen estimators.

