Subgroup analyses for the **composite safety endpoint at Day 5** will use logistic regression, stratified by disease severity at study entry. Within each subgroup, the number and percent of participants with events will be calculated by treatment group, and ORs with 95% CIs comparing the investigational agent versus control will be estimated. Global tests for heterogeneity of the treatment effect across subgroups will be carried out, by testing for interactions between the treatment group and the subgroup variable in an expanded model, as described above. Additionally, subgroup analyses for the composite safety endpoint **through Day 5** will be conducted using Cox proportional hazards models, stratified by disease severity.

Subgroup analyses for **all-cause mortality** and **safety endpoints** that are analyzed using time-to-event methods (through Day 5, Day 28 and through Day 90) will use stratified Cox proportional hazards models, since death is part of the composite endpoints and not a competing risk. HRs will be estimated with 95% CIs for each subgroup, and global tests of heterogeneity of the treatment effect will be carried out, as described above. The proportional hazards models will be stratified by disease severity.

Subgroup analyses for the **pulmonary** and pulmonary+ ordinal outcomes on Day 5 will use proportional odds models, adjusted for the pulmonary or pulmonary+ category at study entry. In order to summarize the distributions across the categories of the ordinal outcome, the mean score (using 1-7 for best to worst) will be calculated by treatment group within each subgroup. For each subgroup, summary ORs with 95% CIs will be calculated. Global tests for heterogeneity of the treatment effect across subgroups will be carried out, as described above.

Subgroup analyses for **time to discharge from the index hospitalization** will use the Fine-Gray model (with death as competing risk), stratified by disease severity at study entry. Similar analyses as described above for time to sustained recovery will be carried out.

Additionally, subgroup analyses will be conducted for subgroups formed by a disease progression risk score at baseline. The construction of this risk score has been published and will be revisited as data on the sustained recovery endpoint accumulate for new investigational agents.¹⁰

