Figure E-1 below shows the data from Table E-4 in a graph. The power of Holm's testing procedure to detect a treatment effect is plotted versus a range of assumed RRRs among the nAb-positive participants (horizontal axis, column 1 of Table E-4); the dashed line shows the

power to detect RRR=1.32 for the nAb-negative subgroup (column 3 in Table E-4), and the solid line shows the power to detect the corresponding treatment effect in the overall cohort (column 4 in Table E-4).

Figure E-1. Estimated power to detect a treatment difference in sustained recovery between AZD7442 and placebo in the overall study population (solid line) and within the subgroup of nAb-negative participants (dashed line), for a range of RRRs among nAb-positive participants and assuming RRR=1.32 for nAb-negative participants.

E-5 Data Analysis Considerations for the Two Co-Primary Hypotheses

The analysis of the primary endpoint will follow the methods described in sections 3 (stratification) and 8.1 (Gray's test for the primary comparisons and Fine-Gray models to estimate RRRs and 95% CIs, stratified by study site pharmacy). The following additional considerations apply to the AZD7442 study:

• The same stratification will be used for testing both co-primary hypotheses. Using blinded baseline data available on January 21, 2022, the strata were determined as follows. To avoid sparse strata, study pharmacies were pooled following the principles described in section 3. Seven strata, each including at least 20 participants in the nAbnegative subgroup, were formed using large sites where possible and combining small sites with each other or with a larger site where that was not. In addition, some very small sites that only enrolled participants who were nAb-positive were combined with one of the 7 strata. For the 99 sites that enrolled at least one participant, the 7 strata will be defined as follows: 1) 3 strata for the 3 U.S. sites that enrolled at least 20 nAb negative participants; 2) 1 stratum for all other U.S. sites; 3) 1 stratum for sites in Denmark, Greece, the United Kingdom, and Singapore; 4) 1 stratum for sites in Spain; and 5) 1 stratum for sites in Uganda.

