- No participants were randomized in disease severity stratum 2 (defined in section 1.2; in particular, stratum 2 included participants requiring invasive mechanical ventilation or ECMO). Therefore, the originally planned stratification of analyses by disease severity stratum can't be carried out. Early in the trial, participants requiring non-invasive ventilation (NIV) or oxygen from a high-flow nasal cannula (HFNC) also were excluded. Beginning July 19, 2021, eligibility was expanded to include participants requiring NIV or HFNC. Considering this expansion of eligibility criteria, a sensitivity analysis will be carried out using a Fine-Gray model that only stratifies by oxygen requirements at baseline. A sensitivity analysis without any stratification will also be carried out.
- A subgroup analysis by calendar date of enrollment will also be carried out (2 subgroups: participants enrolled before July 19, 2021 and at or after July 19, 2021). The cut-point was chosen because on July 19, 2021, the first patient who required HFNC or NIV was enrolled after eligibility was expanded to include such patients.

If the primary comparison of AZD7442 versus placebo for time to sustained recovery shows a significant treatment effect in nAb-negative participants, then major safety, efficacy, and subgroup analyses will be conducted for the nAb-negative participants as well as for the full study cohort.

E-6 Interim Monitoring Guidelines

There are 2 changes to the interim monitoring guidelines described in Section 10.3 of this SAP:

- The information fraction for the Lan-DeMets spending function will be based on the target of 1,228 sustained recoveries, not 843.
- As part of the broad assessment of risk/benefit, the DSMB should consider the findings in nAb negative and nAb positive subgroups. For participants who are nAb negative, greater benefit with the investigational agent is hypothesized.

Comment: The antibody status at baseline was unknown for a large proportion of participants until late in the trial. Therefore, separate interim monitoring boundaries were not planned for this subgroup.

E-7 Subgroup Analyses by Vaccine and Immunosuppression Status

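### The subgroup models in SAP section 9.1, including those for the key nAb hypotheses, leave out site pharmacy, a randomisation factor and a stratum of the primary model; subgroup and overall RRRs are therefore on different bases, and precision is lost if pharmacy or region is prognostic.

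*SAP*

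**What the plan says.** **Randomisation.** SAP section 1.2: "Randomization is stratified by study site pharmacy", with disease severity added only once stratum 2 opens. Section 1.3 names the same two factors.

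**Main comparisons.** Section 8.1 tests sustained recovery with a stratified Gray's test and estimates the RRR with a Fine-Gray model "stratified by disease severity at study entry and study site pharmacy". Section 7 (safety) and section 8.3 (other secondary outcomes) also name both factors.

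**Subgroups.** Section 9.1 gives as its general rule that "subgroup analyses will be carried out using statistical models that are stratified by disease severity". It repeats severity alone for sustained recovery, time to discharge and the Day 5 composite, and for mortality and time-to-event safety: "The proportional hazards models will be stratified by disease severity". The Day 5 ordinal models adjust for the category at entry instead. Pharmacy appears in none of them, and no reason is given.

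**Reach.** Section 9.2 refers its two key nAb hypotheses to the section 9.1 models. Appendix G applies section 9, plus E-7 and E-8, to MP0420 and does not restore pharmacy.

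**Contrast.** Section 3 treats stratification by severity and stratification by severity and site pharmacy as separate terms, and under the second it uses pharmacy when only stratum 1 is analysed. For the AZD7442 overall and nAb-negative tests, E-5 says: "The same stratification will be used for testing both co-primary hypotheses". That stratification is seven pooled site groups. E-5 also records: "No participants were randomized in disease severity stratum 2".

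**The concern.** A trial normally analyses by the factors it randomises by, and this SAP does so everywhere except in the subgroup section and the biomarker models of section 12. Two consequences follow.

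First, a reader will set the nAb-negative RRR beside the overall RRR, and the two would come from differently stratified models. Where only stratum 1 is enrolled, one is pharmacy-stratified and the other is not stratified at all.

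Second, the endpoint is discharge followed by 14 days at home, measured across many hospitals and several countries, so pharmacy or region could plausibly be prognostic. If it is, leaving it out of a Fine-Gray or Cox model pulls subgroup RRRs towards 1 and weakens the treatment-by-subgroup test.

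These analyses carry weight in this platform. Section 1.2 says that nAb-subgroup evidence led to a larger AZD7442 sample and a changed primary analysis. Section 10.2.1 sends nAb subgroups to the DSMB at the early futility review when they are available.

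**Working it through.** **1. Reproduce the plan's own figure.** Section 1.2 plans "90% power to detect a 25% increase in the rate of sustained recovery" at the "0.025, 1-sided level of significance", needing 843 events. Schoenfeld's formula gives 4(1.960 + 1.282)² / (ln 1.25)² = 844.1, rounded up to 845, which is 0.2% from 843. The same formula returns Table E-2 (1,195 events: RRR 1.206) and Table E-3 (542 events: RRR 1.321).

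**2. Interaction power before any pharmacy effect.** Inputs: 485 mITT participants (Appendix G); the planned recovery proportion 843/1,000; a 50/50 nAb split and RRRs of 1.24 and 0.74 from the bamlanivimab trial (section 9.2); two-sided 0.05.
- Events: 485 × 0.843 = 409, or 204.4 per nAb group.
- SE = √(4/204.4 + 4/204.4) = 0.198.
- Effect: ln(1.24/0.74) = 0.516.
- Power = Φ(0.516/0.198 − 1.960) = 74%.

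**3. Add a pharmacy effect.** The trial was simulated with proportional subdistribution hazards, administrative censoring at Day 90 and blocked randomisation within pharmacy, with 800 runs per scenario (Monte Carlo error about 1 to 2 points). Assumptions not in the documents: 60 pharmacies of unequal size; between-pharmacy SD of the log recovery rate as tabulated, half of the variance regional; only stratum 1 enrolled. Simulated recovery was 70–77%. At 76% (the SD 0 case) the step 2 formula gives 70%, close to the simulated 71%.

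Interaction power at N = 485:

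| SD | Pharmacy omitted | 7 pooled strata | Every pharmacy a stratum | Pooled minus omitted |
|---|---|---|---|---|
| 0 | 71.1% | 70.1% | 62.9% | −1.0 |
| 0.25 | 67.5% | 66.7% | 58.3% | −0.8 |
| 0.5 | 59.4% | 64.6% | 58.9% | +5.2 |
| 1.0 | 41.0% | 51.5% | 55.2% | +10.5 |

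**4. Attenuation.** The true ratio of the two RRRs is 1.676 (log 0.516). Shrinkage is 1 − ln(estimated ratio)/0.516.

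| SD | Ratio, pharmacy omitted | Shrinkage | Ratio, 7 pooled strata | Shrinkage |
|---|---|---|---|---|
| 0.25 | 1.645 | 3.6% | 1.664 | 1.4% |
| 0.5 | 1.595 | 9.6% | 1.640 | 4.2% |
| 1.0 | 1.466 | 25.9% | 1.574 | 12.1% |

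At SD 0 there is no shrinkage (ratio 1.703 with and without strata). Pooled strata recover roughly half of the shrinkage, because real differences remain inside each pool.

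**5. What the SDs mean.** At 84.3% recovery the cumulative hazard is −ln(1 − 0.843) = 1.85. The central 95% of pharmacies have hazards 1.85 × exp(±1.96 × SD). Day 90 recovery then spans 68% to 95% at SD 0.25, 50% to 99% at SD 0.5, and 23% to nearly 100% at SD 1.0.

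**6. Type I error.** With no treatment effect, the model without pharmacy rejected the interaction in 5.1%, 4.5% and 5.2% of runs at SD 0, 0.5 and 1.0.

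**7. Larger trial.** At N = 1,000 (400 runs), omitted against pooled power is 94.5% and 94.3% at SD 0, 87.5% and 91.5% at SD 0.5, and 71.8% and 83.3% at SD 1.0.

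**The case against.** The choice can be defended as a trade-off. Section 3's stratification rule covers primary and key secondary outcomes, and only when numbers are large enough. It warns that small strata lose power and prefers severity when strata must be given up. Section 12 also adjusts for severity without pharmacy. Section 9.1 states a general rule, and E-7 and E-8 add or consider further covariates. Section 9.1 already asks for caution because subgroup power is limited. The attenuation is non-collapsibility: the unstratified RRR is a valid quantity, but a different one.

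Much of this stands. It rules out individual-pharmacy strata, which cost 8 to 9 points of power at SD 0 to 0.25. It also means that seven strata should not simply be copied from E-5. At AZD7442's 48%, MP0420 would have about 485 × 0.48 = 233 nAb-negative participants, and a site with 20 of them there would have about 20 × 485/1,417 = 7 here. The nAb-by-antigen cells average 485/4 = 121 people, or 17 per stratum over seven strata, inside the range of 10 to 20 below which section 3 wants pooling.

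It does not justify omitting pharmacy altogether. Section 3 already offers pooling and covariate entry as answers to sparse strata. The E-7 and E-8 covariates do not include pharmacy. Limited power is a reason to keep a prognostic randomisation factor, and the difference in basis from the overall RRR remains whatever the SD.

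**Conclusion.** The point holds as one of consistency and precision. The omission is clear from the text, reaches the key nAb hypotheses and MP0420, and is unexplained. Subgroup and overall RRRs are consequently not on the same basis.

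The loss of power is conditional. It is nil up to an SD of about 0.25, about 5 points at 0.5 and about 11 at 1.0, for N = 485, RRRs of 1.24 and 0.74, and comparison with seven pooled strata. The SDs are assumptions, and the two larger ones imply wide differences in recovery between pharmacies.

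A reader might infer more, and the documents do not support it:
- That subgroup effects are certainly attenuated. No between-pharmacy variation is reported.
- That the interaction test is invalid. Its null rejection rate stays near 5%.
- That the MP0420 subgroup models are certainly unstratified. Stratum-1-only enrolment is recorded for AZD7442 but not stated either way for MP0420.
- That the primary analysis is compromised. It keeps pharmacy.

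**What to change.** In section 9.1, or in Appendix G for MP0420:

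- Stratify the Fine-Gray and Cox subgroup models and their interaction tests by disease severity and by the same pooled site-pharmacy or region strata as the overall MP0420 analysis.
- Fix those strata on blinded baseline data before unblinding, under section 3's pooling rule. Use as few as the nAb-negative subgroup can support, which need not be seven, and do not use individual pharmacies.
- Enter the same pooled strata as covariates in the logistic and proportional odds subgroup models.
- For small subgroups, such as the nAb-by-antigen and nAb-by-RNA cells, collapse to region or use region as a covariate.
- Keep the severity-only model as a sensitivity analysis.

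The cost is a wording change, one blinded pooling step and about 1 percentage point of interaction power if pharmacy or region turns out not to be prognostic.

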9.2 Subgroups by Antibody Serostatus, Plasma Antigen, and Viral RNA Levels

An addendum to the SAP for version 1 of TICO, dated 14 April 2021, described analysis plans for antibody, antigen, viral RNA levels and biomarkers of inflammation and coagulation for monoclonal antibodies studied in TICO. This analysis plan was developed before the corresponding biomarker data were available. Results for the first three investigational agents, bamlanivimab, sotrovimab, and BRII-196/198, were published.¹¹ These analyses informed the current analysis plan for antibody, antigen, and viral RNA data.

This section motivates and describes subgroup analyses by baseline antibody serostatus, plasma antigen levels, and viral RNA levels. Assays are described in Appendix F. Briefly, plasma samples collected at study entry and at days 1, 3 and 5 were used to measure antispike receptor binding domain (RBD) neutralizing antibodies (nAbs) in a surrogate viral neutralization test, anti-nucleocapsid (anti-N) binding antibody levels, and semi-quantitative anti-Spike IgG levels. Qualitative and quantitative plasma SARS-CoV-2 N antigen was measured using a microbead-based immunoassay by Quanterix (Billerica, MA, USA). SARS-CoV-2 viral RNA levels were measured from a mid-turbinate nasal swab. SARS-CoV-2 genome sequencing and variant identification were also determined using Illumina whole genome sequencing of the mid-turbinate nasal swab at baseline.

Statistical models for the subgroup analyses depend on the investigated endpoint, and were described in section 9.1.

The two **key subgroup hypotheses** concern a differential treatment effect (active versus placebo) across subgroups by nAb serostatus for nMAb and antiviral treatments:

- **Hypothesis 1:** Patients who are nAb seronegative (GenScript ELISA) at study entry will benefit more from the investigational agent (compared to placebo) than patients with higher endogenous antibody levels. Furthermore, those who are nAb seronegative AND have high antigen levels will benefit more from the investigational agent compared to placebo than other subgroups categorized by both antibody and antigen levels.
- **Hypothesis 2:** Patients who are nAb seronegative (Genscript) AND have high levels of RNA from nasal turbinate swab will benefit more from the investigational agent compared to placebo than other subgroups categorized by both antibody and RNA levels.

To address these hypotheses, the following subgroups will be considered:

